5.1 Description

Magnesium sulfate is the second most plentiful electrolyte in human intracellular fluids. It has NMDA antagonist and smooth muscle relaxant properties. The medication will appear as magnesium sulfate USP 50%, a sterile, concentrated solution of magnesium sulfate in water. In the vial, each milliliter contains 500 mg magnesium sulfate heptahydrate.

5.2 Treatment Regimen

A loading dose of 50 mg/kg (based on lean body weight) will be administered intravenously over 15 minutes at start of mucosal incision, followed by 25 mg/kg/hr infusion intravenously that is turned off at patient extubation. The expected treatment duration is 1 to 2 hours.

5.3 Method for Assigning Subjects to Treatment Groups

Randomization codes will be generated using web-based randomization software (RStudio) with block sizes of four and an allocation ratio of 1:1 for either intravenous magnesium sulfate (magnesium group) or intravenous normal saline as control (control group). These randomization codes will be enclosed in sequentially numbered, identical, opaque, and sealed envelopes. They will be kept in a closed box during the entire study period. The envelopes will be provided in sequence to the anesthesia team.

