This document is confidential and the property of Stanford University School of Medicine.

8.3.1	Study Sponsor Notification by Investigator	11
8.3.2	EC/IRB Notification by Investigator	12
8.3.3	FDA Notification by Sponsor	12
8.4	UNBLINDING PROCEDURES.....	12
8.5	STOPPING RULES	ERROR! BOOKMARK NOT DEFINED.
8.6	MEDICAL MONITORING.....	12
8.6.1	Internal Data and Safety Monitoring Board	Error! Bookmark not defined.
8.6.2	Independent Data and Safety Monitoring Board	Error! Bookmark not defined.
9	DATA HANDLING AND RECORD KEEPING	12
9.1	CONFIDENTIALITY	12
9.2	SOURCE DOCUMENTS.....	13
9.3	CASE REPORT FORMS.....	13
9.4	RECORDS RETENTION.....	13
10	STUDY MONITORING, AUDITING, AND INSPECTING	13
10.1	STUDY MONITORING PLAN	13
10.2	AUDITING AND INSPECTING.....	14
11	ETHICAL CONSIDERATIONS	14
12	STUDY FINANCES	14
12.1	FUNDING SOURCE	14
12.2	CONFLICT OF INTEREST	15
12.3	SUBJECT STIPENDS OR PAYMENTS	ERROR! BOOKMARK NOT DEFINED.
13	PUBLICATION PLAN	15
14	REFERENCES	15
15	ATTACHMENTS	15

CONFIDENTIAL

This document is confidential and the property of Stanford University School of Medicine.

List of Abbreviations

ESQ – Esophageal symptoms questionnaire

NMDA - N-methyl-D-aspartate

POEM - Peroral endoscopic myotomy

SHC – Stanford Hospital & Clinics

CONFIDENTIAL

This document is confidential and the property of Stanford University School of Medicine.

Study Summary

Title	A prospective, randomized, double-blind, placebo-controlled trial of the effects of magnesium sulfate on postoperative esophageal spasm-associated pain following peroral endoscopic myotomy
Short Title	MgPOEM
Protocol Number	58859
Methodology	Randomized, double-blind, placebo-controlled prospective trial
Study Duration	2 years
Study Center(s)	Single-center
Objectives	This study hypothesizes that among patients having peroral endoscopic myotomy, intraoperative magnesium sulfate infusion will reduce the severity of postoperative pain while decreasing perioperative opioid requirements.
Number of Subjects	100
Diagnosis and Main Inclusion Criteria	Diagnosis: Esophageal motility disorder, including achalasia Main Inclusion Criteria: Patient undergoing peroral endoscopic myotomy
Study Product, Dose, Route, Regimen	Magnesium sulfate. 50 mg/kg (based on lean body weight) intravenous over 15 minutes at start of mucosal incision, followed by 25 mg/kg/hr infusion that is turned off at patient extubation

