4.3 Subject Recruitment and Screening

No patient health information will be collected prior to enrollment. When possible, the primary endoscopist/surgeon or other health care provider(e.g. nurse practitioner, nursing staff) will inform eligible participants of the study. If the patient expresses interest they will be approached by research study personnel. If they decline they will not receive any further information about the study. In cases where it is not feasible for an endoscopist to inform the patients of the study, or the patient has not yet met the endoscopist, a research personnel will screen for eligibility using chart review. Eligible patients will be approached about the study if history review reveals a potential candidate for the study. If the family expresses interest, the research personnel will proceed with consent and protocol. If patient decline interest, we will respect their decision and will not pursue the family any further for this study. Participants will be asked if they are participating in other studies. They will be allowed to participate in more than one study if it can be determined that this poses no increased risk to the participants or the integrity of the data collected for either study.

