5.5 Subject Compliance Monitoring

The anesthesia team will be documenting the drugs in the intraoperative anesthesia medication record. The research staff will review the records to ensure compliance with administration of the study drug. There is no compliance monitoring necessary for the study participant as they will not be administering the drug to or by themselves.

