7.1 Sample Size Determination

Unpublished data at our institution reveals an 60% incidence of esophageal spasm-related pain. We assume that magnesium might decrease the incidence of esophageal spasm-related pain by 30%. Based on this assumption, our calculation show that 45 patients in each group would be necessary to acquire statistical significance, with a two-sided $\alpha = 0.05$ and $\beta = 0.20$. Considering a 10% dropout rate, 50 patients are necessary for each group.

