8.4 Unblinding Procedures

Postoperative magnesium levels evaluated after surgery will reveal those among study participants who received magnesium or normal saline. If a study participant experiences a serious adverse event postoperatively, including cardiorespiratory arrest, unblinding will occur to ensure the patient's safety by evaluating if the patient would benefit from administration of calcium chloride therapy. The patient's randomization envelope contents will be shared with the care team. Documentation of this will be indicated in our data collection spreadsheets. The sponsor will be notified of each participant who was unblinded within 24 hours by phone or email, followed by a written narrative of the event within 48 hours.

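### A fixed block size of four lets up to a third of assignments be deduced by anyone who tracks every earlier arm, and the protocol does not say that recruiting staff lack that access

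*Combined protocol and SAP*

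**What the plan says.** Section 5.3 produces the codes in RStudio "with block sizes of four and an allocation ratio of 1:1". No other block size is mentioned, and nothing says that the size is withheld from site staff or who makes the list and envelopes. The Study Summary gives the study as "Single-center" and no strata are described, so I read this as one list. Section 7.1 concludes that "50 patients are necessary for each group".

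The codes are "enclosed in sequentially numbered, identical, opaque, and sealed envelopes" and go in order to the anesthesia team, which prepares the syringe from the instruction inside (5.4). Only the endoscopist and the patient are stated to be blinded (5.8).

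An arm can also become known after treatment. The anesthesia team charts the drugs given, and "The research staff will review the records to ensure compliance with administration of the study drug" (5.5). Section 8.4 states: "Postoperative magnesium levels evaluated after surgery will reveal those among study participants who received magnesium or normal saline". That level is drawn on the morning after surgery (6.4.1).

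Under 4.3 the endoscopist or another care provider tells patients about the study when possible. Otherwise "a research personnel will screen for eligibility using chart review". Research personnel approach patients and proceed with consent. Section 6.1.1 places screening by phone 24 to 72 hours before surgery.

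**The concern.** Opaque envelopes hide the code inside them. They cannot hide a code that follows from the ones already opened. With one known block size, past arms within a block determine some future ones.

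The documents describe ways in which past arms become visible to people other than the anesthesia team, and they do not separate those people from the ones who recruit. If a recruiter can deduce the next arm, that knowledge can affect whether or when a patient is approached. The groups could then differ at baseline. The primary outcome is the incidence of spasm-related pain at 0 h, which depends on patient report, and it is compared with an unadjusted chi-square test (7.2). That test cannot correct such differences, and foreknowledge cannot be repaired once enrolment is over.

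**Working it through.** The documents give no predictability figure, so there is none to reproduce.

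**Inputs.** Block size 4 and ratio 1:1 (5.3); 50 per group (7.1), so 100 patients, or 25 blocks; one list (inferred from a single centre with no strata).

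**1. Assignments that are certain, with every earlier arm known.** A block holds two magnesium (M) and two saline (S) codes, giving 4!/(2!·2!) = 6 equally likely sequences: MMSS, MSMS, MSSM, SMMS, SMSM, SSMM.
- Position 4 is fixed in 6 of 6 sequences.
- Position 3 is fixed when the first two codes match, in 2 of 6.
- Positions 1 and 2 are never fixed.

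Total: 8 of 6 × 4 = 24 positions, or 33.3%. Over 25 blocks the expected number is 25 × 4/3 ≈ 33, with a possible range of 25 × 1 = 25 to 25 × 2 = 50.

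**2. Best-guess rate.** The observer always names the arm with more places left in the block. The chance of being right is 1/2 at position 1 and 2/3 at position 2. At position 3 it is (1/3)(1) + (2/3)(1/2) = 2/3, and at position 4 it is 1. The mean is (17/6)/4 = 17/24 = 70.8%, against 50% with no information.

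**3. Recent arms unknown.**
- Latest arm missing: only position 4 can be certain, and only if the first two codes match. That is (1/3)/4 = 1/12 = 8.3%.
- Last two missing: at most one arm in the block is known, so 0%.

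**4. Which case is likely.** The documents do not say. As an illustration, assume Poisson arrivals at rate λ and that all arms are known except those from the d days before the approach, with d from 1 to 4. That range reflects contact 24 to 72 hours before surgery and an arm visible the same day or the next. The certain share is about P(0)/3 + P(1)/12, where P(0) = exp(−λd) and P(1) = λd·exp(−λd).
- 100 patients spread over the full two-year study, λ = 100/730 = 0.137 per day: d = 1 gives 0.872/3 + 0.119/12 = 30%; d = 4 gives 0.578/3 + 0.317/12 = 22%.
- Enrolment in one year, λ = 0.274: d = 1 gives 27%; d = 4 gives 14%.

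Cases clustered on the same days would lower these figures.

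**5. Other block schemes**, for an observer who knows every earlier arm and the set of sizes in use:

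| Scheme | Certain | Guessed correctly |
|---|---|---|
| Fixed 4 (as planned) | 33.3% | 70.8% |
| Fixed 6 | 25.0% | 68.3% |
| Fixed 8 | 20.0% | 66.6% |
| Random 4/6 (simulated) | 5.5% | 69.1% |
| Random 4/6/8 (simulated) | 2.3% | 67.9% |

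A second, smaller simulation of random 4/6/8 blocks (300 lists of 100) gave 2.5% and 68%. Varying the size removes most of the certainty but little of the advantage from guessing.

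**The case against.** A reader might infer that a third of assignments are certain in advance and that allocation concealment is defeated. The documents do not support that.

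- The team sure to learn every arm is the anesthesia team, and 4.3 does not name it in recruitment. The endoscopist, who may introduce the study, is stated to be blinded.
- The remaining route is inferred. It needs the research staff of 5.5 to overlap or communicate with the research personnel of 4.3, and the record review to take place while patients are still being enrolled. Section 5.5 gives no timing. Section 8.4 says that magnesium levels reveal the arm, but not that recruiters see them.
- One third needs complete and current knowledge. Because patients are contacted one to three days before surgery, the latest arms may be unknown.
- Each envelope is still sealed, opaque and used in order.

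All of this stands. It limits the size and certainty of the problem but does not remove it: the overlap of roles is not shown, but neither is it excluded, and at about one patient a week the timing gap would often be too short to hide the previous arm.

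A reader might also infer that predictable blocks let the anesthetic be planned around the expected arm. That harm does not come from block size. The anesthesia team is told the current arm by design before it prepares the drug (5.4), and varied blocks would not change that.

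Finally, varying the block sizes alone does little against guessing. This is correct, and it is why the fix has two parts.

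**Conclusion.** The point holds as a weakness in concealment, with moderate confidence. The arithmetic is exact: up to 33.3% of assignments deducible and 70.8% guessable for an observer with the block size, the block boundaries and every earlier arm in the block. The certain share falls to 8.3% or 0% if the last one or two arms are unknown. Whether any recruiter is in that position is not stated. The conclusion rests on one unstratified list, on a drug record that shows which product was given, and on the absence of any text separating recruitment from arm-revealing information. It is worth changing because the change is cheap and the primary outcome is subjective.

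**What to change.** In 5.3, generate the list with randomly varied block sizes, for example 4, 6 and 8, and keep the sizes out of documents available to recruiting and anesthesia staff.

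In 5.3 and 5.5, state that staff who screen or consent do not prepare the list or envelopes, and do not see arm-revealing drug records or magnesium results, until enrolment ends. Existing staff can fill the separated roles. This is the essential half of the fix.

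The cost is a small change to the R code, a few sentences of protocol text and a minor reassignment of record review. Fixed blocks of four end in exact balance at 100. With a largest block of 8, stopping inside a block can leave the arms at most 4 patients apart. No dose, endpoint or sample size changes.

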5.4 Preparation and Administration of Study Drug

The anesthesia team will prepare the study treatment based on the instructions within the envelope. Specifically, the anesthesia team will be instructed to draw up 10 g (20 ml) of the study drug within a 20 ml syringe, or to draw up 20 ml of normal saline within a 20 ml syringe. Although both medications are colorless and transparent, and thus are indistinguishable to the endoscopist, the syringes will be labeled as “study” to minimize drug error during the intraoperative anesthetic management. These medications will be administered using a syringe pump (Alaris; Becton, Dickinson and Company, New Jersey, USA) available in all SHC operating rooms. Instructions to manually program the syringe pump will be provided.

Specifically, the anesthesia team will be instructed to enter 10 g of the study drug in 20 ml of volume, and to enter the patient’s lean body weight. The team will enter the infusion rate as 25 mg/kg/hr, and save these settings.

When the endoscopist announces that she/he will start the mucosal incision, the syringe pump will be programmed to bolus 50 mg/kg over 15 minutes. After the bolus is administered, the syringe pump will default to the infusion rate of 25 mg/kg/hr. The anesthesia team will stop the infusion at extubation.

CONFIDENTIAL

This document is confidential and the property of Stanford University School of Medicine.

5.5 Subject Compliance Monitoring

The anesthesia team will be documenting the drugs in the intraoperative anesthesia medication record. The research staff will review the records to ensure compliance with administration of the study drug. There is no compliance monitoring necessary for the study participant as they will not be administering the drug to or by themselves.

5.6 Prior and Concomitant Therapy

Information on their preoperative medications will be collected, including use of multivitamins, herbal supplements, or magnesium-containing supplements, and use of acid-reducing medications such as H2-receptor antagonists or proton pump inhibitors.

During the study, the patients will be expected to receive standard anesthetic care including hypnotics, narcotics, neuromuscular blockers (e.g. succinylcholine/rocuronium), antiemetics, vasopressors, antihypertensives, and anesthetics as needed at the anesthesia team's discretion. In the rare case of magnesium toxicity, all healthcare providers will have access to calcium chloride/gluconate therapy to reverse the cardiorespiratory and musculoskeletal effects.

5.7 Packaging

As described above, the magnesium sulfate is packaged in 2 ml vials, each containing 1 g (500 mg/ml). Multiple vials are already available in the anesthesia medication carts in every operating room. In addition, the normal saline vials are packaged in 10 ml vials.

5.8 Blinding of Study Drug

The study drug will be blinded to the endoscopist and patient. While the study or control drug is being prepared by the anesthesia team, the endoscopist will not be present in the operating room environment. The 20 ml syringe in which the drug is prepared will be labeled as "study" for the purpose of minimizing drug error during the course of intraoperative management.

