3.1 General Design

- Prospective randomized, double-blind, placebo-controlled trial
- Expected duration of subject participation: 2 days

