5.9.4 Return or Destruction of Study Drug

By the completion of the anesthetic, the drug's bolus and infusion will be documented in the electronic anesthetic record. The unused study drug remaining in the syringe will be wasted and destroyed.

6 Study Procedures

6.1 24 to 72 hours prior to scheduled surgery

- 6.1.1 Patients undergoing per-oral endoscopic myotomy (POEM) in the SHC operating rooms will be identified, and screened by phone whether or not they agree to the study.

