will receive dexamethasone and ondansetron in the aforementioned doses. After surgery, patients will be admitted to the postanesthesia care unit, where opioids (fentanyl and hydromorphone) and antiemetics (anesthesia team's discretion) will be available for further pain and nausea management.

6.3 All study participants will repeat the ESQ in the PACU when the nursing team deems the patient's recovery appropriate enough to participate.

6.4 Postoperative Day 1

6.4.1 The ESQ and serum calcium/magnesium levels will be reobtained in the morning of POD1.

7 Statistical Plan

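### The trial is labeled double-blind, but only the endoscopist and patient are stated to be blinded; the anesthesia team knows the arm, and nothing in the plan keeps outcome collectors unaware of it

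*Combined protocol and SAP*

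**What the plan says.** **Label.** The title reads "A prospective, randomized, double-blind, placebo-controlled trial of the effects of magnesium sulfate", and section 3.1 repeats it: "Prospective randomized, double-blind, placebo-controlled trial".

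**Who is blinded.** Section 5.8 says: "The study drug will be blinded to the endoscopist and patient". No other role is named. Section 5.4 notes that magnesium and saline look alike and "thus are indistinguishable to the endoscopist". It makes no such statement for anyone else. The syringe carries a neutral label, but the stated purpose is to avoid drug error.

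**Who knows the arm.** Section 5.4: "The anesthesia team will prepare the study treatment based on the instructions within the envelope". The same team runs the pump and may give narcotics as it judges necessary (5.6, 6.2.2).

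**What is charted.** Section 5.5: "The anesthesia team will be documenting the drugs in the intraoperative anesthesia medication record". Section 5.9.4 adds that "the drug's bolus and infusion will be documented in the electronic anesthetic record". Section 5.5 also has research staff check these records for compliance. No masked entry or access limit is described.

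**How outcomes are collected.** Under section 6.3, all participants "repeat the ESQ in the PACU when the nursing team deems" them recovered enough. The person who collects pain scores or the ESQ is not named. The ESQ and the magnesium level are both repeated on the morning of postoperative day 1 (6.4.1). Section 8.4 acknowledges that postoperative magnesium levels disclose the arm.

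**PACU text by arm.** Section 6.2.2.2 (magnesium) sets out pain-score thresholds for acetaminophen and opioids and names the antiemetics. Section 6.2.2.3 (control) gives no thresholds, does not mention acetaminophen, and leaves antiemetics to the anesthesia team.

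**The concern.** A reader who sees the double-blind label will assume that those who treat the patient during the outcome window, and those who record the outcome, do not know the arm. The plan secures this for the patient, and for an endoscopist who has no stated part in measuring pain. It does not secure it for the staff who stand between the patient and the data.

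Two kinds of outcome are affected. The primary outcome is the proportion of patients with spasm-related pain at 0 h. It is subjective, no clock time is fixed for it, and section 7.2 does not say how a patient is classified as having such pain. The opioid endpoints depend on clinicians' decisions, and for intraoperative use those decisions are made by a team that knows the arm. A difference between arms could then partly reflect knowledge of the assignment, and a reader would not suspect it.

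**Working it through.** The documents give no figure on this point, so there is nothing to reproduce. The check sets the sections side by side by role and then follows each outcome.

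| Role | Task in the plan | Blinding stated |
|---|---|---|
| Patient | Reports pain and ESQ answers | Blinded (5.8) |
| Endoscopist | Performs the procedure; no stated part in outcome collection | Blinded (5.8) |
| Anesthesia team | Opens envelope, prepares drug, runs pump, gives discretionary opioids, charts (5.4–5.6, 5.9.4, 6.2.2) | Knows the arm by design |
| Research staff | Review the administration record (5.5) | Not stated |
| PACU nurses | Judge when the patient is ready for the ESQ (6.3) | Not stated |
| Collector of pain scores and ESQ | Not named | Not stated |

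**Routes to each outcome**

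- *Pain at 0 h (primary).* The patient is blinded, so knowledge of the arm can act only through when the assessment is made, how answers are elicited or classified, and what other treatment is given around it.
- *Pain and ESQ at 24 h.* The same routes apply, plus one more. The magnesium level that discloses the arm is drawn on the same morning as the ESQ, and nothing orders the two or restricts who sees the result.
- *Intraoperative opioid use.* The decision belongs to the unblinded team, so the exposure is direct. The arm-specific text adds to it: 6.2.2.1 and 6.2.2.3 mention discretionary intraoperative opioids for control patients, while 6.2.2.2 does not mention them for magnesium patients.
- *Later opioid endpoints.* The documents do not say who decides, so the exposure cannot be judged.

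**Hypothetical size for the primary test**

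Inputs from the documents: 60% incidence (7.1); 50 per arm, or 45 after the 10% dropout allowance, since 45/(1 − 0.10) = 50 (7.1); two-sided 0.05 (7.2). Input assumed: a shift b in the recorded rate in the magnesium arm, with no true effect.

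Let x and y be the counts with pain in the control and magnesium arms, and let p̄ = (x + y)/(2n). The uncorrected chi-square test rejects when |Z| > 1.96, where

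Z = [(x − y)/n] / √[p̄(1 − p̄)·2/n].

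The rejection rate is the sum of Bin(x; n, 0.60) × Bin(y; n, 0.60 − b) over all rejecting pairs (x, y).

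| Assumed b | Rates compared | n = 50 per arm | n = 45 per arm |
|---|---|---|---|
| 0 | 60% vs 60% | 5.2% | 4.9% |
| 5 points | 60% vs 55% | 8.5% | 7.2% |
| 10 points | 60% vs 50% | 18.4% | 14.9% |
| 15 points | 60% vs 45% | 34.5% | 28.3% |

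For scale, 10 points in 50 patients is 0.10 × 50 = 5 patients recorded differently.

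**The case against.** The strongest reply is that the patient is blinded and is the source of both the pain score and the ESQ. That stands, and it rules out the view that blinding of the primary outcome is lost. It does not cover timing, elicitation, classification or co-treatment.

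A second reply is that section 8.4 discloses the envelope contents to the care team only after a serious adverse event, which implies that the team is not routinely told. That is fair evidence of intent, but no procedure secures it.

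A third is that section 5.8 says openly who is blinded, and the chart entry may already be masked in practice. Both may be so. The label in the title still says more than section 5.8 does, and the documents are silent on masking.

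A reader might go further and infer the following, which the documents do not support:

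- *That an unblinded person assesses the primary outcome.* The assessor is not named. This is an omission, not a statement that the assessor knows the arm.
- *That PACU nurses control the timing of the primary outcome and give analgesia knowing the arm.* Their only stated role is judging readiness for the ESQ. No section says that they give the analgesia, or that the binary 0 h outcome is derived from the PACU ESQ.
- *That PACU care cannot be delivered without knowing the arm.* The control text is partly an abbreviation of the magnesium text and does not exclude acetaminophen. Followed literally, the difference could reveal the arm; it need not.
- *That the false-positive rates above describe this trial.* The shifts are assumed, and with a blinded patient nothing in the documents makes the larger ones likely.

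**Conclusion.** The point holds in limited form. As written, the plan blinds the patient and endoscopist, has an anesthesia team that knows the arm and charts the drug, and has no provision keeping PACU nurses or outcome collectors unaware. This rests on the text alone and is firm. It is more than missing detail, because the charting, the record review and the arm-specific PACU text could each carry the arm to people near outcome collection.

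The risk to the 0 h outcome is real but indirect, and its size is unknown. The calculation shows only what a bias would do if it were present: at 50 per arm, 5 points would add 8.5 − 5.2 = 3.3 percentage points to the false-positive rate, and 10 points would add 18.4 − 5.2 = 13.2. It assumes 60% incidence, no true effect and an uncorrected chi-square test. The exposure of intraoperative opioid use needs no such assumption, since staff who know the arm make that decision. The plan should be changed, but the gap does not invalidate the design.

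**What to change.** 1. In sections 5.8 and 6.3, state that whoever collects pain scores and the ESQ is blinded, and has no access to an anesthesia record that shows the arm, or to postoperative magnesium results, until the day-1 ESQ is complete.
2. Where the record system allows, chart the infusion under a neutral study-drug entry. The envelope route in section 8.4 remains for emergencies.
3. Do the section 5.5 compliance review after outcome collection, or assign it to existing staff who do not collect outcomes.
4. Describe blinding by role in the title, section 3.1 and section 5.8, with the anesthesia team stated to be unblinded. Report intraoperative opioid use as an outcome decided by unblinded staff; the steps above do not protect it.
5. Reconcile the PACU passages in 6.2.2.2 and 6.2.2.3. I take no view on which is right.

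The cost is protocol wording, a minor charting change whose feasibility the documents do not establish, and a less favorable description of the blinding. No added staff are needed.
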